### **8.7.4 Early Withdrawal Visit**

Subjects who have early withdrawn from the study should complete the early withdrawal visit within 7 days after the investigator's awareness (if it is less than 7 days from the date of the

previous visit, repeated tests of the same item can be waived), excluding subjects who have early withdrawn from the study due to withdrawal of consent or are lost to the follow-up.

At the early withdrawal visit, the following procedures will be performed:

- Subjects must be fasted before each visit (fast for at least 10 hours overnight without depriving of water);
- Vital signs;
- Physical examination;
- 12-lead ECG;
- Laboratory tests: including hematology, blood chemistry, urinalysis, coagulation function test, and urine pregnancy test (only for women of childbearing potential);
- Weight measurement and Ccr calculation;
- Collect blood samples for exploratory analysis (one blood sample each for inflammatory indicators and PD biomarkers; among these, 5 mL of blood is collected for PD biomarker testing and sent to the central laboratory for testing);
- Exploratory skeletal muscle mass and function assessment: including ASMI, muscle strength (grip strength) and 6-meter walking speed test (specific test indicators are subject to the actual operation of each center). Among them, ASMI is detected and calculated by DXA, and the calculation formula is ASMI = appendicular muscle mass (kg) / height (m^2);
  - Return diary card;
- Return investigational product;
- MDS-UPDRS Part III score before the administration of background medication for PD (only applicable to subject who has received stable medication for PD within at least 4 weeks prior to study entry, and this score should be  $\geq$  12 hours from the most recent dose of background medication for PD);
- Take background medication for PD (only applicable to subject who has received stable medication for PD within at least 4 weeks prior to study entry);
- MDS-UPDRS score: Parts I, II, III, IV (if the subject has received stable medication for PD within at least 4 weeks prior to study entry, Part III score must be assessed at

$2 \pm 1$  hours after the administration of background medication for PD at this visit);

- Record concomitant medications/therapies;
- Record AEs;

### **8.7.5 Unscheduled Visit**

If a subject participates an unscheduled visit at the study site, it should be documented accordingly.

## **9 AE-related Assessment**

### **9.1 Definition of AEs**

#### **9.1.1 AEs**

An AE is any untoward medical occurrence in a patient administered an investigational product (TJ0113 capsules or placebo) and which does not necessarily have to have a causal relationship with this treatment. It can manifest as symptoms, signs, diseases or laboratory test abnormalities. Therefore, the AE can be any unfavorable or unexpected, or clinically significant symptoms, signs or diseases, including ADRs, important laboratory abnormal findings, new diseases during the study, and exacerbation of pre-existing conditions or symptoms (excluding the conditions to be treated with the investigational product; daily fluctuation in underlying disease is not considered as an AE).

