#### **2.3.2.5 Drug Interactions**

TJ0113 may cause CYP induction in vitro and, therefore, may reduce exposure levels to drugs metabolized by CYP enzymes. The in vitro induction of human CYP450 enzymes by TJ0113 showed that within the concentration range of 0.2-10  $\mu$ M, TJ0113 did not significantly induce the expression of CYP1A2, CYP2B6, and CYP3A4 messenger ribonucleic acid (mRNA) in human hepatocytes from the two donors of HUB and BEI; TJ0113 showed a concentration-

dependent induction effect on the expression of CYP1A2, CYP2B6, and CYP3A4 mRNA in human hepatocytes from Lhuf15906 donors within the concentration range of 1-10  $\mu$ M.

The in vitro inhibitory effect study of TJ0113 on human CYP450 enzymes showed that following the administration of TJ0113, the half inhibitory concentrations (IC50) for CYP1A2, CYP2D6 and CYP3A4 (midazolam and testosterone as substrates) were greater than 50  $\mu$ M, and the IC50 for CYP2B6, CYP2C8, CYP2C9 and CYP2C19 were 23.1  $\mu$ M, 24.7  $\mu$ M, 10.8  $\mu$ M and 38.3  $\mu$ M, respectively, and there was no significant inhibitory effect on all the CYP enzyme isoforms.

TJ0113 had very low intestinal permeability and may be a substrate for other efflux transporters in addition to being a weak substrate for the efflux transporter P-gp. In addition, MDCK-OAT1 and HEK293-URAT1 cell lines were used to study the inhibitory effect of TJ0113 on organic anion transporter 1 (OAT1) and urate transporter 1 (URAT1), and the transport effect of transporters OAT1 and URAT1 on TJ0113. The study results showed that TJ0113 inhibited transporter OAT1 significantly, with an IC50 of 4.32  $\mu$ M; there was no significant inhibitory effect on transporter URAT1, with an IC50 greater than 30  $\mu$ M. TJ0113 was not a substrate of transporter OAT1, and it might be a substrate of transporter URAT1.

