#### 7.2.1 Permitted Concomitant Medications/Therapies

Concomitant medications/therapies allowed to be administered from signing of the ICF to 1 week after the last dose of the investigational product include:

- Background medications for PD that have been stably used for at least 4 weeks before study entry, of which the treatment regimen can remain unchanged (for subjects who have used any background medications for PD including levodopa, if any AE such as dyskinesia occur, the dose of levodopa is allowed to be reduced at the discretion of the investigator);
- Other concomitant medication or therapies that have already been used at the time of screening, of which the original drug/therapy type, dose or treatment frequency and setting should remain unchanged as much as possible;
- Drugs required to be used for treating the AEs.

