#### **9.1.4 Serious Adverse Events (SAEs)**

An SAE refers to any adverse medical event that results in deatha, is life-threatening eventb, requires hospitalization or prolongation of existing hospitalization for the subjectc, results in persistent or significant disability/incapacityd, or is congenital abnormality or birth defecte, or is other important medical eventf after the subject uses an investigational product.

Further explanations for the above criteria are as follows:

- a. An AE that results in subject's death;
- b. An AE in which the subjects was at risk of death at the time of the event; it does not refer to an event which hypothetically might have caused death if it were more severe (e.g., drug-induced hepatitis without liver failure);
- c. Any AEs resulting in hospitalization or prolongation of existing hospitalization (hospitalization: refers to that a subject has been admitted at the inpatient department

or emergency ward for observation or treatment over 24 h; prolongation of existing hospitalization: the AEs occur during hospitalization period and prolong the existing hospitalization), excluding elective surgery or admission for examination, etc., decided prior to study participation and for which the treatment is not changed.

- d. The consequences of the AE may cause serious inconvenience or interference with the subject's normal life and activities, cause impairment, damage or destruction of the subject's physical function and/or physiological structure, physical activities or quality of life;
- e. It is suspected that exposure of a parent to the study drug may cause malformation or congenital functional defect, etc., in the subject's offspring;
- f. Medical and scientific judgment must be exercised in deciding whether expedited reporting is appropriate in other situations, such as important medical events that may not be immediately life-threatening or result in death or hospitalization but may be considered serious if medical intervention is necessary to prevent one of the above situations. For example, important treatment in emergency room or allergic bronchospasm at home, cachexia or convulsion requiring no hospitalization, development of drug dependence or addiction etc.

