#### **9.4.2 Reporting of SAEs**

For all SAEs that occur within the collection time limit specified in this protocol, the investigator must fill in, sign and date the SAE Report Form within 24 hours of awareness, immediately report it to the sponsor (or the CRO appointed by the sponsor).

In case of reports involving death events, the investigator should provide the sponsor and Ethics Committee with other necessary information, such as autopsy report and final medical report.

The investigator should provide detailed written follow-up reports in a timely manner. For follow-up information of SAEs, the reporting method and time limit are the same as those for the initial report.

Time for collecting SAEs:

- Only SAEs related to protocol-specified procedure or invasive test, etc. will be reported from subject's signing ICF to the first dose of the investigational product.
- The investigator needs to collect and report all SAEs (regardless of whether it is causally related to the investigational product or related to clinical procedure) from the first dose of the investigational product to the end of the follow-up period;
- SAEs that occur after the end of the clinical trial or the end of the follow-up until the conclusion of the review and approval is obtained, if assessed by the investigator that the relevance to the investigational product cannot be ruled out, should be informed to the sponsor (or the CRO appointed by the sponsor) within 24 hours of awareness.

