## **9.5 Reporting of Special Conditions**

### **9.5.1 Death**

Regardless of relevance to the investigational product, all deaths during the trial must be recorded as SAE (including death due to the disease proposed to be treated with the investigational product) and reported to the sponsor (or a CRO appointed by the sponsor) within 24 hours of awareness.

Death should be regarded as the outcome rather than a separate event. Death is not reported as SAE term, but the cause of death must be reported as the SAE term. Information of events leading to death can also be further improved in follow-up reports. The term "sudden death" is used only to describe where a subject with or without pre-existing heart disease died suddenly and accidentally within 1 hour of onset of the acute symptoms, and the cause of death is presumed to be the heart disease; or the subject died without any witness within 24 hours after the subject is last seen (when the subject's vital signs are stable). If the cause of death cannot be determined at the time of reporting, the SAE term may be recorded and reported as "death

unexplained". If the cause of death is subsequently established (e.g., after an autopsy), the SAE term should be replaced with the established cause of death.

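### The AE definition excludes worsening of Parkinson's disease, so a serious worsening not attributed to study drug can go unrecorded as an AE or SAE

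*Protocol*

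**What the plan says.** - **AE definition (Protocol 9.1.1).** The definition includes "exacerbation of pre-existing conditions or symptoms", followed directly by the limit "excluding the conditions to be treated with the investigational product; daily fluctuation in underlying disease is not considered as an AE". Adverse drug reactions (ADRs) are listed separately in the same sentence, before that limit.
- **SAE definition (Protocol 9.1.4).** It opens with "An SAE refers to any adverse medical event that results in" and lists the seriousness criteria. The note on hospitalisation reads "Any AEs resulting in hospitalization or prolongation of existing hospitalization". The notes on death, life-threatening events and disability are also worded in terms of an AE. The only exception stated within the hospitalisation note is for elective surgery, examinations and the like, settled before the patient joined the study.
- **Recording and reporting (Protocol 9.4.1.2, 9.4.2).** Investigators record and report events that meet the AE or SAE definition. The 24-hour duty is set out "For all SAEs that occur within the collection time limit specified in this protocol".
- **Death (Protocol 9.5.1).** Every death during the trial is an SAE, "including death due to the disease proposed to be treated with the investigational product".
- **SAP.** Section 3.3.1 takes its AE definition from Protocol Section 9. Section 6.12.2 summarises only treatment-emergent AEs (TEAEs), with rows for serious events and for TEAEs that led to withdrawal. Section 6.3 tabulates reasons for early withdrawal among all randomised patients.

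**The concern.** Daily fluctuation has its own clause in 9.1.1. The clause on the treated condition must therefore remove something more than routine variation, and the natural reading is any worsening of PD. Nothing outside the death rule says expressly that a hospitalised, life-threatening or disabling worsening of PD is an AE or SAE.

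In a blinded trial the investigator usually cannot tell a drug effect from the course of the disease in one patient. Only the comparison between arms can show it, and that comparison needs the events recorded in all arms whatever cause is assigned to them. If recording depends on suspecting the drug, the comparison is made on a filtered subset. This matters here because the completed clinical trial described in Protocol 2.4 was in healthy subjects, who could not show worsening of PD.

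**Working it through.** No formula underlies the point. The check is to read the sections in order for one case: a patient is admitted for marked motor worsening, and the investigator judges it unrelated to study drug.

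1. **Is it an AE?** It is an exacerbation of a pre-existing condition, but that condition is the one under treatment. Under 9.1.1 it is excluded. It is not an ADR, because 9.1.5 and 9.2 require a relationship that cannot be ruled out.
2. **Is it an SAE?** The opening of 9.1.4 is broad enough to include it. The note on hospitalisation starts from an AE, which step 1 denies. The two parts of 9.1.4 point in different directions.
3. **Must the site record or report it?** Under 9.4.1.2, only if it meets a definition, so the answer inherits the ambiguity of step 2. Sections 9.4.1.1 and 9.4.2 require collection whatever the causality from first dose to the end of follow-up, but only of events that already qualify as AEs or SAEs.
4. **Does it reach the SAP tables?** SAP 3.3.1 adopts the protocol definition and 6.12.2 counts only TEAEs. If the event is not an AE, it is absent from the TEAE and serious-event summaries.
5. **If the patient withdraws instead of being admitted?** Withdrawal is not a seriousness criterion for any event, so no 24-hour report is lost. What is lost is the AE record and the entry among TEAEs that led to withdrawal. The withdrawal still appears with its reason under SAP 6.3.

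**Can the efficacy data stand in?** Only in part.
- Scheduled on-treatment ratings fall on D7, D28, D56 and D84 (Protocol 1.2). The gaps are 28 − 7 = 21 days, 56 − 28 = 28 days and 84 − 56 = 28 days.
- MDS-UPDRS is also scored at the early withdrawal visit (Protocol 8.7.4). That visit is not expected after withdrawal of consent or loss to follow-up, and the analysis visits listed in SAP 6.1 are baseline and V3 to V6 only.
- An unscheduled visit has only to be documented (Protocol 8.7.5); no rating is required.

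**Size.** Each arm has about 50 patients, so one missed patient is 1/50 = 2% of an arm. The documents give no rate of serious PD worsening over 12 weeks, so no expected count can be derived.

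**The case against.** The best reply is that the gap is narrower than it looks, and much of that reply stands.

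- **The SAE opening is wide.** It does not use the defined term AE, and PD admissions are not among the stated exceptions. A careful site could report them. This makes the text ambiguous; it does not settle it, because the explanatory notes speak of AEs.
- **The ADR route.** ADRs are listed in 9.1.1 outside the exclusion, so worsening suspected to be drug-related can enter, and can be an SAE if serious. This stands. It leaves the worsening judged unrelated.
- **The event is not wholly lost.** Withdrawal reasons are tabulated, anti-PD medication is recorded with indication and dates (Protocol 7.2) and summarised (SAP 6.8), and the early withdrawal visit includes MDS-UPDRS. None of these carries the severity grade, causality and seriousness of an AE record, and the withdrawal data miss a patient who is admitted but stays in the trial.

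A reader might also infer more than the documents support:

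- **That 9.5.1 contradicts 9.1.1.** It is a special rule for deaths beside a general definition. That it names PD death shows only that one case was thought of.
- **That 7.2.1 contradicts 9.1.1** because it says "if any AE such as dyskinesia occur, the dose of levodopa is allowed to be reduced". The documents do not call dyskinesia a worsening of PD, and the scale scores motor complications in a separate part.
- **That TJ0113 is likely to worsen PD by lowering background drug levels,** since 2.3.2.5 says it "may reduce exposure levels to drugs metabolized by CYP enzymes". The same section reports no significant induction of the tested enzymes in cells from two of three donors, all in vitro, and no background PD drug is identified as a substrate. The point does not need this argument.

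**Conclusion.** The concern holds in a limited form. As written, the protocol allows a serious worsening of PD that is not attributed to study drug to be left out of AE recording, 24-hour reporting and the SAP's TEAE and serious-event tables, and it allows sites to treat the same admission differently. For withdrawals, the loss is confined to AE recording and the tables built on it.

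It would go too far to say that every PD admission is certainly outside SAE reporting, or that only a death brings PD worsening in. The opening of 9.1.4 and the ADR route both argue against that.

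The conclusion assumes that the exclusion attaches to the exacerbation clause it follows, and that sites apply the AE-based notes in 9.1.4 as written. The number of patients affected is unknown and could be zero; each would be 2% of an arm. The change is worth making because it improves safety ascertainment at little cost.

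**What to change.** In Protocol 9.1.1, keep the carve-out for daily fluctuation and replace the blanket exclusion with a recording rule. Worsening of PD is an AE, whatever its suspected cause, when it:

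- meets any seriousness criterion in 9.1.4;
- leads to a change in study drug or in anti-PD treatment; or
- leads to early withdrawal.

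When it is serious it is an SAE and is reported within 24 hours. State that a change in MDS-UPDRS score alone remains an efficacy measure. Align 9.1.4 and 9.5.1 with the rule, so that the opening of 9.1.4, its notes and the death rule all say the same thing. The SAP definition needs no new text, because SAP 3.3.1 follows Protocol Section 9.

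This concerns recording and reporting only and does not touch how patients are managed. The cost is a wording amendment and a line in the eCRF completion guide. The downside is a few more AE and SAE records, some of which will overlap with the efficacy endpoint.

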#### **9.1.2 Treatment-Emergent Adverse Events (TEAEs)**

A TEAE refers to any AE that emerges during treatment (absent pre-treatment) or worsens relative to the pre-treatment state after the first dose of the investigational product.

#### **9.1.3 Treatment-Related Adverse Events (TRAEs)**

A TRAE refers to any TEAE related to the investigational product at the investigator's discretion.

#### **9.1.4 Serious Adverse Events (SAEs)**

An SAE refers to any adverse medical event that results in deatha, is life-threatening eventb, requires hospitalization or prolongation of existing hospitalization for the subjectc, results in persistent or significant disability/incapacityd, or is congenital abnormality or birth defecte, or is other important medical eventf after the subject uses an investigational product.

Further explanations for the above criteria are as follows:

- a. An AE that results in subject's death;
- b. An AE in which the subjects was at risk of death at the time of the event; it does not refer to an event which hypothetically might have caused death if it were more severe (e.g., drug-induced hepatitis without liver failure);
- c. Any AEs resulting in hospitalization or prolongation of existing hospitalization (hospitalization: refers to that a subject has been admitted at the inpatient department

or emergency ward for observation or treatment over 24 h; prolongation of existing hospitalization: the AEs occur during hospitalization period and prolong the existing hospitalization), excluding elective surgery or admission for examination, etc., decided prior to study participation and for which the treatment is not changed.

- d. The consequences of the AE may cause serious inconvenience or interference with the subject's normal life and activities, cause impairment, damage or destruction of the subject's physical function and/or physiological structure, physical activities or quality of life;
- e. It is suspected that exposure of a parent to the study drug may cause malformation or congenital functional defect, etc., in the subject's offspring;
- f. Medical and scientific judgment must be exercised in deciding whether expedited reporting is appropriate in other situations, such as important medical events that may not be immediately life-threatening or result in death or hospitalization but may be considered serious if medical intervention is necessary to prevent one of the above situations. For example, important treatment in emergency room or allergic bronchospasm at home, cachexia or convulsion requiring no hospitalization, development of drug dependence or addiction etc.

### **9.1.5 Adverse Drug Reactions (ADRs)**

All noxious and unintended responses to a medicinal product related to any dose should be considered Adverse Drug Reactions (ADRs). There is at least a reasonable possibility of the causal relationship between the investigational product and an AE, i.e., the relationship cannot be ruled out.

For a new medicinal product or new usage, all harmful or unexpected reactions at any dose causally related to administration of the drug in clinical use before approval, particularly in the period when therapeutic dose has not been determined should be considered ADRs.

### **9.1.6 Suspected Unexpected Serious Adverse Reactions (SUSARs)**

SUSARs refer to suspected unexpected serious adverse reactions whose clinical manifestations are beyond the Investigator's Brochure for the investigational drug, package inserts for marketed medicinal products, summary of product characteristics and other existing information in terms of their nature and severity.

Assessment of expectedness: It should be assessed based on the relevant sections of the Investigator's Brochure for the investigational product that is effective at the date of the event, which serves as the safety reference information. Unexpected, for the investigational product, means that the event is not listed on the Investigator's Brochure of the investigational product, or the nature or severity of the event exceeds that described in the Investigator's Brochure of the investigational product.

## 9.2 Causal Relationship

The investigator should conduct a comprehensive analysis according to the specific circumstances of AEs of the subjects and their past medical history, concomitant diseases and concomitant medications, to determine the correlation between AEs and the investigational product. The investigator should perform causality analyses for treatment-emergent symptoms in order to identify potential correlations between the AE and the investigational product.

The specific criteria for adjudicating the causal relationship between the AE and the investigational product are shown in Table 9-1. The causal relationship between the AE/SAE and investigational product is judged as definitely related, probably related, possibly related, unlikely related and not related. Among them, "definitely related, probably related, and possibly related" are classified as related to the investigational product, and this type of AEs are regarded as ADRs. "Unlikely related and not related" are classified as unrelated to the investigational product, and this type of AEs will not be included in ADR analysis.

